6.1 Clinical Background – Atrial Fibrillation

Atrial fibrillation (AF) is the most common, clinically significant, cardiac tachyarrhythmia, affecting more than 33 million patients worldwide, with a projected incidence of 5 million patients per year.(1) In the United States alone, approximately 6 million individuals suffer from AF and over one million new cases are diagnosed annually; due to the aging population, the number is expected to double by the year 2030.(2, 3)

AF is associated with a substantially increased risk of stroke and thromboembolic events, primarily due to the Left Atrial Appendage (LAA) serving as a site for thrombus formation(4). Untreated patients with AF have a 2-5% annual incidence of stroke, with a history of stroke or thromboembolic events conferring an even higher risk.(5, 6) Strokes that occur with AF are large and can be quite debilitating, leading to death or costly and painful rehabilitation as well as adding significant financial burden to the medical system.

6.2 Current Standard of Care to Treat Atrial Fibrillation

The standard treatment for stroke prevention in subjects with AF is oral anticoagulant (OAC) therapy to reduce the likelihood of clot formation, which is recommended regardless of the management strategy of the underlying rhythm disorder.(7) Options include warfarin and the direct oral anticoagulants (DOACs) (dabigatran, rivaroxaban, apixaban, and edoxaban).(8-11) While pharmacotherapy can reduce stroke incidence in AF by approximately 60%,(12) OAC therapy is associated with an increased risk of bleeding complications,(13) an issue of significant concern due to the high bleeding risk of many AF patients. In addition, management of OAC therapy is burdensome and long-term compliance is poor, leaving patients at risk for embolic events.

Echocardiographic evidence that the LAA is the source of thrombi in more than 90% of patients with AF has prompted the development of novel transcatheter therapies to occlude the LAA, (14-18) The WATCHMAN® Left Atrial Appendage Closure Device (Boston Scientific Corporation, Marlborough MA) was the first Left Atrial Appendage Occlusion (LAAO) device to be extensively studied in patients. The WATCHMAN device is a self-expanding nitinol structure with a polyethylene face. The device is constrained within the delivery system until deployment within the LAA. Randomized clinical trials demonstrated the WATCHMAN to have acceptable benefit to risk ratios for LAA closure in patients with non-valvular AF and a high risk for stroke or systemic embolism and an appropriate rationale to seek a non-pharmacologic alternative to oral anticoagulation.(7, 19) The WATCHMAN device received FDA approval in March 2015 on the basis of data from the PROTECT-AF(20) and PREVAIL (19) randomized clinical trials and associated continued access registries that demonstrated that the device was non-inferior to warfarin for the primary composite endpoint of stroke, systemic embolism, or cardiovascular death. In addition, when compared to the warfarin control arm, patients receiving the WATCHMAN device had approximately 80% reduction in hemorrhagic strokes and a >50% reduction in cardiovascular death. (7, 19)

A second-generation WATCHMAN Device, the WATCHMAN FLXTM, was developed to simplify LAAO and was studied in the Pinnacle Study, a single arm study which showed comparable performance.. (21) Based on the Pinnacle study results, the WATCHMAN FLX received FDA approval in July 2020.(22) Recently, Abbott Laboratories (Abbott Park, IL) received FDA Approval for the Amplatzer Amulet Left

Atrial Appendage Occluder.(23) The Amulet consists of a lobe and disk connected by a flexible waist and is constructed from a nitinol mesh and a polyester patch. The Amulet is deployed using a similar procedure as the WATCHMAN and comes in 8 sizes..(24)

While LAA closure with the WATCHMAN and Amplatzer devices represents an important advance in stroke prevention for patients with AF, important limitations remain. These include the need for precise measurement of LAA diameter and depth, precision coaxial delivery, frequent residual leaks and anatomic features which make LAAO difficult to achieve.

The stroke risk for patients with AF has been extensively studied. The Swede Afib study examined the stroke risk in 180,000 untreated AF patients from 2005-2008 and further validated the CHA₂DS₂-VASc as seen in the figure below.(25)

[figure not shown]

Figure 1: Extracted from European Heart Journal (2012) 33, 1500-1510(25)

These data have allowed prediction of the rate of strokes for subjects enrolled in the CONFORM Trial if untreated medically or without LAAO. Assuming a CHA₂DS₂-VASc score of 4.5 (the observed score reported for subjects recruited to the AMULET(26) and Pinnacle Trials(21)) the stroke risk is ~6% per year based upon the Swede Study. We expect the stroke risk to be similar in subjects who are enrolled in the CONFORM Trial. The poor acceptance of OAC was also highlighted by the Swedish study which showed that >45% of subjects with indication for OAC (CHA2DS2-VASc ≥2) were untreated. These data underscore the need for alternatives to traditional pharmacologic treatment such as LAAO. Presently, there are only two LAAO implantable devices available which have the limitations listed above. Therefore, additional options for patients and caregivers are needed.

Conformal Medical, Inc (Nashua, NH), the CONFORM study sponsor, has developed the CLAAS System to address these limitations of the first generation LAAO devices. Early experiences with the CLAAS System have been published (27, 28) and an updated brief summary of the studies are provided below.

6.3 Conformal Prague Study

The Prague Feasibility Study was designed to evaluate the safety and performance of the CLAAS System. The study was performed at a single center in Prague, Czech Republic (Homolka Hospital). Subjects were treated using a conscious sedation protocol which featured Intracardiac Echo (ICE) guided transseptal puncture and device deployment with TEE confirmation prior to final release. Subjects were followed through hospital discharge and through serial follow-up assessments post index procedure at discharge, 7 days, 45 days including TEE imaging, 6 months, and 12 months including TEE imaging. The primary safety endpoint of the study is freedom from major adverse events while the primary performance endpoint is LAA closure success. A total of 15 subjects were recruited from October 2019 through January 2020, when the study was paused due to the COVID-19 Pandemic. Results of these initial 15 subjects were summarized by Turagam et al. (27)

A total of 15 subjects (age 71.3±10.8 years, 33% men, CHA2DS2-VASc of 4.1 ±1.7, HAS-BLED 3.4 ±1.4) underwent LAAC, 100% successfully. There were no procedure/device-related complications requiring intervention. Asymptomatic pericardial effusion occurred in 2 subjects. The 45-day, 6-month, and 12-month follow-up imaging in 11, 9, and 13 subjects, respectively, revealed adequate LAA seal (leak <5 mm) in all subjects; device-related thrombus was detected in 1 subject at 6 months. Over 1-year follow-up, there were no ischemic strokes and 1 minor bleed. Non procedure-/device-related death occurred in 2 subjects.

Following removal of COVID-19 restrictions, an additional 4 subjects were treated. Preliminary results indicate successful closure without procedural complications in all subjects. Additional details on this study will be available in the study Investigator Brochure.

6.4 US Early Feasibility IDE Clinical Study

The CLAAS System was also evaluated in the United States as part of an Early Feasibility IDE Clinical study (EFS) which has been performed in two phases. The first phase is being performed at five (5) clinical sites. A total of 22 subjects were enrolled in the initial phase with 18 subjects successfully implanted with the CLAAS Implant.

The first phase EFS cohort was summarized by Sommer et al.(28) Twenty-two subjects (63.7% with CHA2DS2-VASc scores ≥3, 76.2% with HAS-BLED scores ≥3) were enrolled. The device was successfully implanted in 18 subjects and unsuccessfully in 4 subjects. There were no serious procedural complications. On transesophageal echocardiography performed at 45 days, 1 significant leak (≥5 mm) was seen, which was due to a large posterior lobe not appreciated at the time of implantation, and one device-related thrombus was noted, which resolved on oral anticoagulation. There were no periprocedural strokes, major pericardial effusions, or systemic or device embolization. This phase was performed with the Large CLAAS Implant available for only the last subject. The four subjects with unsuccessful closure were treated prior to the availability of the Large Device and were found to have an LAA that was too large for the Regular Device.

The second phase of the EFS included an additional 42 subjects with 41 successful implants. There has been one reported periprocedural complication of a pericardial effusion requiring treatment. As of August 2024, there have been no reported leaks > 5 mm at 45 days post procedure. The 45-day follow-up imaging in 34 subjects revealed adequate LAA seal (leak < 5mm) in all subjects; device-related thrombus was noted in two subjects at 45 days post procedure. There has been no device embolization, ischemic strokes, or deaths reported.

The combined clinical experience supports the feasibility of LAA Occlusion with the CLAAS System; demonstrating the full functionality of the system including device delivery, retrieval and release; and supports the further evaluation of the product in a pivotal trial.

7 Investigational Device

7.1 Name of the Investigational Device

The CLAAS® System

7.2 Manufacturer

Conformal Medical, Inc. [name]

7.3 Clinical Trial Indication for Use

The CLAAS system is intended to reduce the risk of thromboembolism from the left atrial appendage in patients with non-valvular atrial fibrillation who:

- Are at increased risk for stroke and systemic embolism based on CHADS₂ or CHA₂DS₂-VASc scores and are recommended for oral anticoagulation (OAC) therapy; AND
- Are deemed by their physician to be suitable for OAC; AND
- Have an appropriate rationale to seek a non-pharmacological alternative to OAC, taking into account the safety and effectiveness of the device compared to OAC.

7.4 Device Description

The following is a summary description of the Investigational Device. For additional information, please refer to the Instructions for Use.

7.4.1 Overview

The CLAAS System delivers a plug to the ostia of the Left Atrial Appendage (LAA) and is designed to occlude the appendage to eliminate blood flow (Figure 1). The Implant is pre-attached to the CLAAS Delivery Catheter and loaded by the user into the CLAAS Delivery Catheter (Figure 4) at the time of the procedure. The Delivery System consists of:

- 1) CLAAS Delivery Catheter with Implant and Loading Cone (Figure 4),
- 2) Access Sheath with Dilator (Figure 3)

The system is designed to track through the vascular anatomy from the femoral vein to the LAA. The system includes an Access Sheath with Dilator to accommodate vascular access using a standard femoral vein approach to the right atrium, across the atrial septum, and into the LAA. Echocardiography and fluoroscopy are used during the procedure to verify sizing and to aid in deployment of the Implant to the target location.

[figure not shown]

Figure 2: CLAAS Delivery System and Implant in LAA anatomy

[figure not shown]
7.4.1.1 Initial CLAAS and Next Generation CLAAS Systems

The Initial CLAAS System (including the access sheath, delivery catheter, and implant) was used from the beginning of the study enrollment in June 2022 through the end of April 2024. In April 2024, Conformal initiated several changes to the CLAAS System, referred to in this Clinical Investigational Plan as Next Generation CLAAS. These included reducing the height of the anchors on the implant, modifying the orientation of the ePTFE layers of the implant, improving the kink resistance and torque transmission of the Access Sheath and Delivery Catheter, reducing the stiffness of the dilator, and redesigning the delivery catheter handle to improve ergonomics, reliability, and performance.

7.4.1.2 CLAAS Implant

The CLAAS Implant is designed to conform to the geometry of the LAA and is delivered via a percutaneous Delivery System. The implant is designed to permanently seal off the LAA from the LA with an endothelial layer that forms across the LA face of the implant. The implant is available in two different sizes; Regular (27 mm) and Large (35 mm) to accommodate patient anatomy. Angiography and/or echocardiography at the time of the procedure may be used to determine the LAA ostium diameter to properly select the Implant size (Table 1). The implant has an inner, cylindrical, Nitinol endoskeleton (frame) that provides the mechanical base structure (#4 in Figure 3). The Nitinol endoskeleton contains 10 face struts and 20 anchors (Regular size) and 12 struts and 24 anchors (Large size) facing proximally to engage the tissue to resist movement. The endoskeleton also provides the conformable structure to enable the foam cylinder (#2 in Figure 3) to compress against the LAA tissue to facilitate sealing.

CLAAS Implant

- 1. ePTFE Outer Cover thromboresistant surface
- 2. Foam Body
- 3. Foam Bumper 5mm height
- 4. Endoskeleton
- 5. Anchors 2 rows; 10/row for Regular 27mm CLAAS or 12/row for Large 35mm CLAAS
- 6. Bumper Markers (x4 within the Bumper)
- 7. Shoulder Marker (for placement reference)
- 8. Tether
- 9. Tether Pin

Figure 3: CLAAS Implant Components

Table 1: CLAAS Implant sizing

Implant Size	Mean LAA Ostium Diameter (D _{max} + D _{min}) / 2	LAA Ostium Diameter Range	Minimum Landing Zone Depth
Regular	≤ 25 mm	10 – 33 mm	10 mm
Large	≤ 32 mm	20 – 40 mm	10 mm

7.4.1.3 Delivery System

The CLAAS system is delivered to the target location at the LAA ostium using standard interventional techniques and imaging to ensure appropriate placement and sizing. Under echocardiographic guidance, a transseptal puncture is used to place an Access Sheath. A pigtail catheter may be advanced over a guidewire via the Access Sheath into the LAA to perform an angiogram of the LAA. In addition, Echocardiography is also used at the time of the procedure to guide the sizing and delivery of the implant.

Delivery of the Implant is achieved with a customized coaxial delivery system (nominal dimensions provided in Table 2). Vascular access is achieved with the Conformal Access Sheath with Dilator (nominal dimensions provided in Table 3). The Implant is loaded into the distal end of the CLAAS Delivery Catheter as outlined in the Instructions for Use. The system is designed with sufficient length to access the LAA from a femoral vein puncture. The CLAAS Delivery Catheter working length is designed such that when it is locked to the Access Sheath, its distal tip is about 3cm short of the Access Sheath tip. This allows the user to advance the Implant from the CLAAS Delivery Catheter into the Access Sheath prior to deploying it into the subject. The Delivery System includes the Access Sheath with Dilator and the CLAAS Delivery Catheter. The Delivery System components are shown in Figure 4.

The Access Sheath and Dilator systems are provided in two different sizes to accommodate the different implant sizes and are also offered as either single or double curves to accommodate varying vascular anatomy. The Single Curve Access Sheath has a single, 90-degree bend at its distal end with a radius of 3.5 inches. The Double Curve Access Sheath has a double curve, which is an anterior curve distal to the primary curve. The Access Sheath components are shown in Figure 5. The VizaraMed Multiflex Steerable Sheath 15.5F has been evaluated for compatibility with the Regular (27 mm) CLAAS System and may be used as an alternative to the Regular Conformal Access Sheath. The 15.5F VizaraMed Multiflex Steerable Sheath is not compatible with the Large (35 mm) CLAAS System.

Table 2: CLAAS Delivery Catheter Nominal Dimensions

Component	Regular	Large		
CLAAS Delivery Catheter				
Outer diameter	15.2F	17.1F		
Inner diameter	13.3F	15.3F		
Working length	73cm	73cm		

Table 3: CLAAS Access Sheath Nominal Dimensions

Component	Regular	Large
Access Sheath		
Outer diameter	17.8F	19.8F
Inner diameter	15.7F	17.6F
Working length	77.5cm	77.5cm

[figure not shown]

Figure 4: CLAAS Delivery Catheter with Implant and Loading Cone

[figure not shown]

Figure 5: Single curve CLAAS Access Sheath with Dilator components

7.4.1.4 Device Traceability

Refer to the CLAAS System IFU and packaging labels for additional device identification and information.

It is estimated that each study subject undergoing the CLAAS System implant procedure will require one device to be implanted. The final number of devices used during the index procedure may be dependent upon factors, such as individual patient anatomy and procedural considerations.

A description regarding how traceability shall be achieved during and after the clinical investigation is outlined in **Section 17**.

7.4.1.5 Control Devices

The control devices for the study will be commercially available transcatheter LAAO devices. Currently, there are four FDA approved LAAO devices (WATCHMAN, WATCHMAN FLX and WATCHMAN FLX Pro from Boston Scientific; and Amulet from Abbott Laboratories) all of which can be used in subjects assigned to the Control Group. It is anticipated that additional transcatheter devices may gain FDA approval during the enrollment period of the study. When a new transcatheter LAAO product becomes commercially available, its suitability for subjects assigned to the Control Group will be assessed by the Executive Committee; and with approval by FDA, the newly available control device will be added and included in an updated protocol which will be submitted for IRB/REB/EC approval.

The control devices will be placed in accordance with the approved Instructions for Use and all subjects will be managed through the same follow-up timeframe as the treatment device in accordance with the FDA approved labeling for post procedure anticoagulation/antiplatelet medication.

8 Study Design

8.1 Study Objectives

The pivotal trial has four objectives:

Objective 1: To evaluate the safety and effectiveness of the CLAAS System by demonstrating non-inferiority to currently marketed LAAO systems in subjects with non-valvular atrial fibrillation.

Objective 2: To demonstrate the safety of a post procedure pharmacologic antiplatelet regimen that consists of DAPT alone without concomitant anticoagulation therapy.

Objective 3: To demonstrate the ability to safely deliver the CLAAS Device using a conscious sedation protocol without general anesthesia. To investigate this objective, a separate Sub-Study will be conducted after recruitment of the RCT is complete at select, qualified sites based on the experience demonstrated in the RCT.

Objective 4: Support regulatory approval(s) in territories outside US.

8.2 Study Design and Rationale

The CLAAS system is designed to provide the benefits of left atrial appendage closure with a conventional device, while potentially simplifying the implantation procedure, improving procedural safety, and reducing the peri-device leakage. The study will evaluate the safety and effectiveness of LAA closure with the CLAAS system in subjects with non-valvular atrial fibrillation who are at increased risk for stroke and systemic embolism.

This is a pivotal clinical trial that includes three components: (1) a Roll-In Phase using the CLAAS system alone, (2) a Randomized Clinical Trial (RCT) comparing CLAAS to commercially available LAAO systems, and (3) a subsequent, single arm Sub-Study investigating the use of conscious sedation; conducted after enrollment in the RCT is complete and listed under a separate NCT number within the clinicaltrials.gov website (NCT06049615).

- **8.2.1 Roll-In Phase:** To ensure adequate implant experience, up to 300 subjects study-wide may be implanted with the CLAAS Implant as roll-in cases, Investigational sites that implanted 3 subjects with the Initial CLAAS system will be permitted to implant one additional subject with the Next Generation CLAAS System. Additional investigational sites will be permitted to implant up to a maximum of 3 roll-in subjects (Initial CLAAS System and Next Generation CLAAS System combined).\(\)\). Data from roll-in subjects will be included in a comprehensive summary of safety but will not be included as part of the primary analysis dataset (ITT). All Roll-in subjects will have the same data collection and follow-up requirements as randomized subjects. The results of the Roll-in cohort will be compared with the CLAAS subjects from the RCT group to characterize the product learning curve.
- **8.2.2 Randomized Controlled Trial**: A prospective, unblinded, randomized, multicenter, active control trial to evaluate the safety and effectiveness of the CLAAS System by demonstrating non-inferiority against standard of care, commercially available LAA occlusion devices. The RCT will be performed in a staged manner with no more than 250 subjects treated in the initial phase to support a safety summary on the first 50 CLAAS implants. Once approved by FDA, the RCT will advance to the second stage of enrollment completing recruitment of the RCT cohort.
- **8.2.3 Conscious Sedation Single Arm Sub-Study:** A prospective single arm trial evaluating a conscious sedation protocol. The sub-study will evaluate the safety and performance of the CLAAS device using conscious sedation in comparison with the device delivery safety and performance observed in the CLAAS arm of the RCT. The sub-study will be performed in

accordance with all protocol requirements and all subjects will be evaluated for a primary endpoint based on the product performance at the 45 Days post procedure. Enrollment in the sub-study will not commence until enrollment in the randomized cohort is complete, initial safety of the CLAAS system is confirmed by the DSMB and FDA and FDA approval of the Sub-Study has been granted through an IDE Supplement.

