8.3 Number of Required Subjects

The sample size requirements for each of the study cohorts:

8.3.1 Roll-in Phase: Up to 300 subjects study-wide may be implanted with the CLAAS Implant as roll-in cases, Investigational sites that implanted 3 subjects with the Initial CLAAS system will be permitted to implant one additional subject with the Next Generation CLAAS System.

Additional investigational sites will be permitted to implant up to a maximum of 3 roll-in subjects (Initial CLAAS System and Next Generation CLAAS System combined). The number of cases is determined through the training and proctoring process and is based upon demonstrated proficiency.

- **8.3.2 RCT Phase**: Up to one thousand six hundred (1600) subjects will be enrolled in the randomized control trial. The sample size is based on the power requirements for the primary effectiveness endpoint and was determined via simulation. With a non-inferiority margin of 3.2%, and one-sided alpha level of 0.025, the sample size of 1600 subjects should provide approximately 85% power for the hypothesis test of non-inferiority accounting for a 10% attrition rate. This sample size is also expected to provide greater than 80% power for the hypothesis test for the primary safety endpoint with a margin of 5.8% and a one-sided 0.025 alpha level. It should be noted that >50%_of the subjects enrolled in the RCT phase will be from the US and no more than 15% of the data will be from one site.
- **8.3.3 Conscious Sedation Single Arm Sub-study:** The sub-study is designed to demonstrate non-inferiority in CLAAS Implant success compared to the CLAAS arm of the RCT based on the 45 Day Endpoint. It is estimated that a total sample size of 130 subjects (including 6% attrition) is required to demonstrate non-inferiority. This estimated sample size will be verified and adjusted,

if necessary, based on the observed rate of CLAAS Implant success rate in the RCT, prior to initiation of the sub-study. Appendix E provides a summary of the Sub-Study with statistical rationale. This Sub-Study will be identified with a separate NCT number from the randomized controlled trial (NCT06049615).

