8.8.1 Roll-In Population

A Roll-In ITT subject is an individual who signs an ICF, is assigned to the Roll-In Cohort by the site and has an implant procedure attempted. For this population, an implant procedure attempt (ITT established) is defined when the LAAO Access Sheath is introduced into the body.

If an implant procedure is attempted without an implant placed, the subject must be followed through the Primary Safety and Efficacy Endpoints (at all visits including 7-days, 45-days, 6-months, 12-months, and 18-months) assessing only: QVSFS, AE Assessment, and Concomitant Medication Assessment. These assessments can be conducted via telehealth/phone call. These subjects will not be required to have subsequent protocol mandated imaging and will not be required to follow the medication requirements. If a subject in the Roll-in population experiences a suspected stroke or systemic embolism, the subject should be brought in for an Unscheduled Visit (in-person clinic visit) for assessment per the Schedule of Assessments matrix. After the 18-Month visit, these subjects will have completed all required study assessments.

Subjects who are scheduled for a roll-in procedure, but no longer meet eligibility criteria and do not have a procedure attempt (i.e., the access sheath never entered the body) will be followed only through 45 days via telehealth/phone call visits. No protocol mandated imaging or medication therapy will be required. After the 45-Day visit, these subjects will have completed all required study assessments and will be classified as Screen Failures.

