8.8.3 Randomized Population

A Randomized subject is an individual who signs ICF and is found to meet all eligibility criteria and is randomized. When a subject is randomized, he/she will be included in the Intention to Treat population.

The Randomized Population includes two groups: 1) subjects who undergo LAAO Procedure and 2) subjects who after randomization and prior to the study procedure are found to no longer meet eligibility criteria. Examples include subjects after randomization while awaiting the procedure fall and sustain a fractured hip. Also included are subjects who are brought to the Cardiac Catheterization Laboratory who on baseline TEE evaluation are found to have thrombus in the LAA.

Subjects who are randomized, no longer meet eligibility criteria (group 2 above) must be followed through the Primary Safety and Efficacy Endpoints with telehealth/phone call visits (at all visits including 7-days, 45-days, 6-months, 12-months, and 18-months) assessing only: QVSFS, AE Assessment, and Concomitant Medication Assessment.

These subjects will not be required to have subsequent protocol mandated imaging and will not be required to follow the medication requirements. If a subject in the Randomized Population group experiences a suspected stroke or systemic embolism, that subject should be brought in for an Unscheduled Visit (in-person clinic visit) for assessment per the Schedule of Assessments matrix. After the 18-Month visit, these subjects will have completed all required study assessments.

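### The learning curve is to be read from roll-in versus RCT CLAAS subjects, but roll-in status only roughly marks early experience and is confounded with device generation

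*Protocol*

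**What the plan says.** Section 8.2.1 sets the method in one sentence: "The results of the Roll-in cohort will be compared with the CLAAS subjects from the RCT group to characterize the product learning curve". It names no case order, operator, site or device-generation term. Roll-in data go into the safety summary and stay out of the primary dataset.

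Other sections define who the roll-in subjects are:

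- **Numbers (8.2.1, 8.3.1).** A site that has implanted three subjects with the Initial system "will be permitted to implant one additional subject with the Next Generation CLAAS System". Other sites have a maximum of three over both generations, with no stated minimum. The study-wide cap is 300. Section 8.3.1 adds: "The number of cases is determined through the training and proctoring process and is based upon demonstrated proficiency".
- **Assignment (8.8.1).** A roll-in subject "is assigned to the Roll-In Cohort by the site and has an implant procedure attempted".
- **Device (7.4.1.1).** The Initial system was used from June 2022 to the end of April 2024. The Next Generation changes begun in April 2024 included "reducing the height of the anchors on the implant", and also altered the ePTFE layers, access sheath, delivery catheter, dilator and handle.
- **Generation analyses (14.2, 14.7).** Analyses of Initial versus Next Generation recipients, and a device-type subgroup analysis, are planned. Neither is linked to the learning-curve comparison.

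**The concern.** A learning curve asks how results change as a site or operator does more cases with a given device. Comparing roll-in with RCT CLAAS subjects answers that only if roll-in means early, RCT means late, and little else differs between the cohorts. The protocol's own rules weaken each condition, and the device itself changed partway through.

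At stake is how the sponsor describes the learning curve. Improvement due to the redesign could be credited to experience, or a real experience effect could be masked by the mix of generations. Either would mislead readers who draw lessons for training and proctoring.

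**Working it through.** The protocol gives no figure for this comparison, so there is none to reproduce. The check sets the rules side by side and then uses illustrations with assumed rates.

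**1. Is roll-in early?** Mostly, probably, but not always. Enrollment began in June 2022 and the Next Generation system dates from April 2024, about 22 months later. A site that finished three Initial roll-ins could have treated RCT CLAAS subjects before its extra Next Generation roll-in. That order is inferred from the dates; it is not stated.

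**2. Is RCT late?** Not always. Roll-ins are capped per site, not per operator, so a second operator's first CLAAS case can be an RCT case. Section 9.3 anticipates sponsor review of the initial five cases at sites without appropriate CLAAS experience. If those are CLAAS cases, that exceeds the three roll-ins allowed to an additional site.

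**3. Do the cohorts weight sites alike?** Inputs from the Synopsis: up to 100 + 5 + 15 = 120 sites, at most 300 roll-ins, up to 1600 randomized 1:1, and no more than 15% from one site.

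- Roll-ins per site: 300/120 = 2.5.
- RCT CLAAS subjects per site: 800/120 = 6.7.
- One site's largest share of 300 roll-ins: 3/300 = 1.0% to 4/300 = 1.3%.
- One site's largest share of the RCT: 15%.

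The site mix can therefore differ widely. Because roll-in numbers depend on proficiency, slower sites may also supply more roll-ins.

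**4. What can generation mix do alone?** Assume no learning, a complication rate p_I with Initial and p_N with Next Generation, and Initial shares f_R in roll-in and f_C in RCT CLAAS. The apparent learning effect (roll-in minus RCT) is

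D = (f_R − f_C) × (p_I − p_N).

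| p_I, p_N (assumed) | f_R = 0.8, f_C = 0.4 | f_R = 0.4, f_C = 0.6 | f_R = f_C |
|---|---|---|---|
| 6%, 4% | 0.4 × 2 = +0.8 points | −0.2 × 2 = −0.4 | 0 |
| 8%, 4% | 0.4 × 4 = +1.6 | −0.2 × 4 = −0.8 | 0 |
| 10%, 5% | 0.4 × 5 = +2.0 | −0.2 × 5 = −1.0 | 0 |

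The sign depends on which cohort holds more Initial devices. In the middle row, a real learning effect of 0.8 points would be exactly cancelled under the second set of shares.

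**5. What can a late roll-in do?** Assume a true complication rate at site case k of 4% + 6% × exp(−(k−1)/3), over ten cases, with experience carrying across generations.

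- Roll-ins are cases 1–3: mean 8.46% against 5.00% for the other seven, a difference of 3.5 points.
- Roll-ins are cases 1, 2, 3 and 7: mean 7.55% against 5.04% for the other six, a difference of 2.5 points.

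The curve has not changed, but the contrast shrinks by about 1 point. If learning instead restarts with the new system, case 7 is a first case, and pooling two generation-specific curves is the problem. On either assumption, cohort membership does not recover the curve.

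**The case against.** The strongest reply is that this is one sentence in a design section. It fixes no analysis set, covariate or test, and Section 14 leaves detail to an SAP that is not shown and may well use case order or generation. Generation analyses are already planned, so a device effect is less likely to go unnoticed. Most roll-ins will be a site's first CLAAS cases. No hypothesis, margin or success criterion uses the comparison.

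Much of this stands, and it keeps the point small. What remains is that the protocol itself names cohort membership as the measure of learning and does not connect the generation analyses to it.

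Four stronger readings are tempting but unsupported:

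- **Mismatched denominators.** For roll-ins, "an implant procedure attempt (ITT established) is defined when the LAAO Access Sheath is introduced into the body", whereas for the RCT, "When a subject is randomized, he/she will be included in the Intention to Treat population". A reader might infer that unlike sets will be compared. Section 8.2.1 does not say that RCT ITT applies, and the Attempted Population in 8.8.4 matches the roll-in definition. The mismatch is a risk only if ITT is chosen.
- **A count of misclassified roll-ins.** One might call every extra Next Generation roll-in wrongly labelled early. The protocol permits these cases without requiring them, does not say how many sites will use the rule, and such a case is early if the count restarts with the new system.
- **The early feasibility results.** The rise from 18 of 22 to 41 of 42 implants might look like learning. Section 6.4 attributes the four failures to appendages too large for the Regular device before the Large size was available, so the figures show neither experience nor the 2024 redesign.
- **Easier or harder roll-in cases.** Site assignment makes this possible, but nothing in the protocol shows a difference in difficulty, and the proposed analysis would not remove one.

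**Conclusion.** The point holds as a limited one. Roll-in versus RCT CLAAS is an imperfect contrast of early with late experience and is confounded with device generation, so it can give a false learning effect or hide a real one.

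Its size and direction cannot be derived from the protocol, which gives neither the generation shares by cohort nor the case order. The range of -1.0 to +2.0 points and the shrinkage from 3.5 to 2.5 points rest wholly on the assumed rates, shares and curve; they show what is possible, not what is expected.

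A reader might infer that the non-inferiority result is at risk. It is not: roll-ins are outside the primary dataset and neither primary endpoint uses this comparison. This is an inexpensive improvement to a descriptive analysis.

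**What to change.** Amend Section 8.2.1 to say that:

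1. The learning curve will be assessed in Attempted subjects (access sheath inserted) from both the roll-in cohort and the RCT CLAAS arm.
2. Results will be examined by sequential CLAAS case number within site, counting roll-in and RCT CLAAS cases together, and within operator if the implanting operator is recorded on the eCRF.
3. Results will be presented separately by, or stratified by, device generation (Initial or Next Generation).
4. The simple roll-in versus RCT summary is descriptive only.
5. Selection of roll-in subjects by the site remains a limitation of the analysis.

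Roll-ins stay out of the primary ITT analysis as planned. No extra subjects or visits are needed. Section 17 already has implanted CLAAS devices recorded on the CRF; the sponsor should confirm that device generation can be identified from that record and whether the operator is captured. The cost is a little more analysis work and smaller numbers in each stratum.
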